9.2 Handling of Intercurrent Event and Missing Data

9.2.1 Missing Data due to COVID-19 and Logistical Problems (Geo-political Restrictions)

Missing data could occur due to various reasons, including missing visits/assessments, early withdrawal from the study, or missing due to COVID-19 infection or logistic restriction, as well as due to logistical problems (geo-political restrictions).

The COVID-19 pandemic is interfering with the conduct of many ongoing trials, with potential impacts on treatment duration and the collection, analysis, and the interpretation of clinical trial data. Some protocol-specified visits in the clinical trials may be impacted due to COVID-19 infection or logistical restrictions during the pandemic. Impacted visits due to COVID-19 will be recorded in the database. The probability of having missed visits and missing data due to COVID-19 infection or logistical restrictions related to the COVID-19 pandemic can be reasonably assumed to be unrelated to the unobserved values. Therefore, for the purpose of statistical analysis, it is reasonable to assume that these missing data are missing at random (MAR) and the statistical models that require MAR assumption are appropriate. Sensitivity analyses will be performed to assess the impact of missing data and the robustness of the conclusion. The same logic is likely applicable to data missing due to logistical problems (geo-political restrictions) so that the MAR assumptions is also applicable.

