Subjects who develop malignancy other than NMSC or carcinoma in-situ of the cervix must be discontinued from the study drug. Information including histopathological results should be queried for the confirmation of the diagnosis.

Management of Demyelinating Disease

Subjects must be discontinued from study drug with new onset and/or radiographic evidence of central nervous system demyelinating disease (including multiple sclerosis), optic neuritis, and peripheral demyelinating disease (including Guillain Barré syndrome).

Management of Hypertension

Subjects should be closely monitored for the development of hypertension. Investigators should consider stopping the study drug if hypertension is not successfully controlled under standard of care.

Management of Hyperglycemia

Subjects should be closely monitored for the development of hyperglycemia. Investigators should manage the hyperglycemia with appropriate standard of care.

Management of Glucocorticoid Induced Adrenal Insufficiency

Subjects should be closely monitored for signs and symptoms of adrenal insufficiency (e.g., nausea, vomiting, lightheadedness, pale skin, unexplained weight loss, low blood pressure, electrolyte abnormalities [e.g., confirmed hyponatremia < 135 mmol/L, hyperkalemia > 5.5 mmol/L], etc.) and if adrenal insufficiency is suspected, further clinical assessment and management should follow local standard of care and may include measuring of cortisol levels and/or ACTH stimulation test to be performed at a local laboratory. Glucocorticoid therapy with physiologic doses should be considered. After withdrawal of glucocorticoid therapy, adrenal insufficiency may persist for months; therefore, glucocorticoid therapy should be considered in any situation of stress (e.g., serious infection) occurring or in the months following withdrawal of study drug.

Management of COVID-19

Subjects should be closely monitored for COVID-19. Study drug should be interrupted if a subject develops a confirmed diagnosis of COVID-19. Consider the interruption of study drug in subjects with signs and/or symptoms and suspicion of COVID-19.

Management of Select Laboratory Abnormalities

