9.2.2 Handling of missing data in Categorical Endpoints

- Non-Responder Imputation incorporating multiple imputation to handle COVID-19 and logistical problems (geo-political restrictions) (NRI-MI) will be the primary approach to handle missing data for categorical endpoints. The

NRI-MI will categorize any subject who does not have an evaluation during a pre-specified visit window (either due to missing assessment or due to early withdrawal from the study) as a non-responder for the visit. The only exceptions are: 1) when the subject is a responder both before and after the visit window, where the subject will be categorized as a responder for the visit, and 2) when the data is missing due to COVID-19 infection or logistical restriction, or logistical problems (geo-political restrictions), which will then be handled by Multiple Imputation. Subjects whose change/percent change from Baseline cannot be calculated because of a missing Baseline will be considered as a non-responder at all post-baseline visits in NRI-MI approach.

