- **Multiple Imputation (MI):** a sensitivity analysis for the primary endpoint: Markov Chain Monte Carlo (MCMC) will be first applied to augment data into monotonic missing pattern and PROC MI will be used to generate 30 datasets using the regression method. The variables to be included in the imputation model for the Placebo-Controlled Period are treatment group, stratification factors at randomization [Baseline glucocorticoid (yes/no), number of prior failed b/tsDMARDs (1; 2 or more), and a combined prior anti-TNF failure/adalimumab use factor (prior anti-TNF failure with adalimumab use; prior anti-TNF failure without adalimumab use; no prior anti-TNF failure)], Baseline, and measurements at each visit in the Placebo-Controlled Period. The variables to be included in the imputation model for the LTE periods are treatment group, major stratum [baseline glucocorticoid use (yes/no) and prior adalimumab use (yes/no)], Baseline, and measurements at each visit in the LTE periods. The random seed for MCMC and the random seed for PROC MI are specified in Appendix C. The imputed post-baseline measurements will be rounded to the same precision as the observed data before the determination of responder status. Subjects will be characterized as responders or non-responders based on the MI imputed datasets. Using the Cochran-Mantel-Haenszel (CMH) model adjusted by stratification factors [Baseline glucocorticoid (yes/no), number of prior failed b/tsDMARDs (1; 2 or more), and a combined prior anti-TNF failure/adalimumab use factor (prior anti-TNF failure with adalimumab use; prior anti-TNF failure without adalimumab use; no prior anti-TNF failure)], the imputed endpoints will be analyzed using each of the 30 datasets. SAS PROC MIANALYZE will be used to generate the

final inferences of the risk difference between each ABBV-154 group and placebo.

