9.3.3 Sensitivity and Supplementary Analyses of the Primary Efficacy Endpoint(s)

A sensitivity analysis of the primary analysis of the primary efficacy endpoint will be conducted using the MI method for handling missing data.

An additional analysis will be conducted where the baseline definition for patient's assessment of pain, PtGA, PhGA, and HAQ-DI is updated to where values collected up to 7 days after the day of first dose may be considered for the baseline value.

A separate analysis may be performed in the ITT Population excluding subjects who have major protocol deviations in the Placebo-Controlled Period. The subject exclusion criteria for this analysis will be finalized before unblinding data for the Primary Analysis.

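### Week 12 data missing because of COVID-19 infection are imputed as missing at random, and the one planned missing-data sensitivity analysis makes the same assumption, so it cannot test it

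*SAP*

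**What the plan says.** SAP 9.2.1 makes one argument for two kinds of pandemic missingness, infection and logistics. For both, it says that the chance of a missed visit or missing value "can be reasonably assumed to be unrelated to the unobserved values". It concludes that MAR methods are appropriate, extends the reasoning to geo-political disruption, and promises sensitivity analyses of the effect of missing data on the conclusion.

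SAP 9.2.2 makes non-responder imputation with multiple imputation (NRI-MI) the primary method for categorical endpoints. A missing visit counts as non-response with two exceptions. One is a subject who responds both before and after the visit window. The other is "when the data is missing due to COVID-19 infection or logistical restriction, or logistical problems (geo-political restrictions), which will then be handled by Multiple Imputation".

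Only one imputation model is described: "The variables to be included in the imputation model for the Placebo-Controlled Period are treatment group, stratification factors at randomization", followed by the baseline value and the measurements at each visit of the period. Appendix C gives separate random seeds for NRI-MI and for the MI sensitivity analysis, but no second model.

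Protocol 6.2 says: "Study drug should be interrupted if a subject develops a confirmed diagnosis of COVID-19". SAP 8.0 considers no intercurrent events.

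On robustness, SAP 9.3.3 says: "A sensitivity analysis of the primary analysis of the primary efficacy endpoint will be conducted using the MI method for handling missing data". The other two analyses in that section concern the baseline window and, optionally, the exclusion of major protocol deviations.

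**The concern.** For a closed site or a travel restriction, it is reasonable to treat missingness as unrelated to the value that would have been seen. Infection is different because the event that causes the missed visit may also interrupt treatment and make the subject acutely ill. Either could change the Week 12 joint counts, hsCRP and patient-reported scores that make up ACR50. The imputation model has no term for infection or interruption, so it predicts the missing value from subjects of the same arm with a similar history, whether or not they were interrupted.

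If lost dosing lowers response, the imputed active-arm rate would be too high. The placebo rate would be less affected, because interrupting placebo removes no active drug. The difference could then be overstated. The primary-analysis response rates also feed the dose-response modelling in SAP 9.6, where the minimum effective dose is set against a 22% target, so a shift of a point or two near that target is of some interest.

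The clearer gap is in the robustness check. SAP 9.2.1 promises one, but the analysis specified does not vary the assumption in question.

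**Working it through.** **1. The two analyses side by side, for a missing Week 12 ACR50**

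| Reason missing | Primary (NRI-MI) | Sensitivity (MI) |
|---|---|---|
| COVID-19 infection | MI under MAR | MI under MAR |
| COVID-19 or geo-political logistics | MI under MAR | MI under MAR |
| Any other reason | Non-response* | MI under MAR |

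*Unless the subject responds both before and after the window.

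The first two rows do not change apart from random seeds. The third row moves towards MAR. The sensitivity analysis therefore tests non-responder imputation for the other missing data and says nothing about infection-related data. The non-responder imputation in SAP 9.5 applies after Week 12, so it is not a check on the primary endpoint.

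**2. The plan's own figure**

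Inputs from SAP 2.4: 85 per group, placebo 13%, difference 22 points (so active 35%), two-sided alpha 0.1, chi-square test, power at least 90%.

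Power = Φ{[0.22√85 − 1.645√(2 × 0.24 × 0.76)] / √(0.13 × 0.87 + 0.35 × 0.65)} = Φ{(2.028 − 0.993) / 0.584} = Φ(1.77) = 96.2%.

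The stated figure is met and is not in dispute.

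**3. Size of a possible bias**

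The documents give no infection-related missing rate, so the following are assumptions: fa = 2-8% of an active arm (1.7 to 6.8 of 85 subjects), fp = 2-3% of the placebo arm, and infected active subjects who would respond at the placebo rate of 13%.

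- MAR imputation: 0.35 − 0.13 = 22.0 points, whatever fa and fp are.
- True difference: 0.35(1 − fa) + 0.13fa − 0.13 = 0.22(1 − fa). With fa = 2% this is 21.6 points, and with fa = 8% it is 20.2.
- Bias of MAR: 0.22fa, which is 0.4 to 1.8 points.
- Non-responder imputation: 0.35(1 − fa) − 0.13(1 − fp). The lowest value, at fa = 8% and fp = 2%, is 0.3220 − 0.1274 = 19.5 points. The highest, at fa = 2% and fp = 3%, is 0.3430 − 0.1261 = 21.7 points.

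Non-responder imputation is thus a contrasting assumption rather than the truth. At the high corner it slightly exceeds the true value (21.7 against 21.6), and at the low corner it falls below it (19.5 against 20.2). It lies below the MAR figure throughout this range.

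**4. Effect on power**

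Assumed missingness of 2%, 5% and 10% was tried. The 10% results are the lowest:

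| Scenario at 10% missing | Difference | Power |
|---|---|---|
| Active-arm missing respond at placebo rate | 19.8 points | 92.9% |
| Non-response, equal missingness in both arms | 19.8 points | 93.8% |
| Non-response, missingness in active arm only | 18.5 points | 90.1% |

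**The case against.** The best defence is that interruption does not by itself make MAR wrong. Dosing visits fall every two weeks up to Week 12 (Protocol Appendix E), so a subject infected after the Week 10 dose has missed no dose due before the Week 12 visit. A subject infected earlier who recovers and attends has an observed value, and nothing is imputed. SAP 10.2.1 equates 70 days with five half-lives, about 14 days each, so one skipped dose is not full loss of exposure. The model also conditions on earlier visits, so a decline that has already been observed carries into the imputation.

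Most of this stands, and it limits the claim to doubt. It does not close the gap. In Appendix E the last joint counts and hsCRP before Week 12 are at Week 8. A subject infected between Week 8 and Week 10 could miss the Week 10 dose and then the Week 12 visit, with no later measurement in the placebo-controlled period for the model to use. Acute illness at Week 12 is also unmodelled, whether or not a dose was missed.

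Two stronger readings are tempting and are not supported:

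- A reader might infer from Protocol 2.2, which links TNF antagonists and glucocorticoids to serious infection, that unequal infection rates between arms break MAR. They do not, because treatment group is in the imputation model. The same section also says that the drug's effects on the course of COVID-19 are not well defined.
- A reader might give infected active subjects 0% response and leave infected placebo subjects at 13%, which at 8% missing yields 0.35 × 0.92 − 0.13 = 19.2 points. That scenario is inconsistent: an illness that removes all response would do so in both arms, and the answer would then be the non-responder figure.

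**Conclusion.** The point holds as a gap in the robustness check and a doubtful assumption. It is not a demonstrated bias. The plan applies MAR to infection-related missing data although the protocol links infection to drug interruption, and its single missing-data sensitivity analysis leaves that assumption untouched.

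On the assumed rates (2-8% of an active arm missing because of infection, response at the 13% placebo rate), the overstatement would be about 0.4 to 1.8 points on 22. Power was at least 90% in every case tried, so the sample size is not threatened. The direction, in favour of active treatment, is what one would expect if lost dosing lowers response, but the documents do not establish it.

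A reader might go further and conclude that MAR is false for infection, or that the primary method must change. Neither follows. MAR remains defensible for logistical and geo-political missingness. NRI-MI is also the primary method named in Protocol 7.4, and scoring infection as non-response is an untested assumption of its own. It is useful as a contrast, not as a replacement.

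**What to change.** Keep NRI-MI as the primary analysis. Add to SAP 9.3.3 one sensitivity analysis of ACR50 at Week 12 with the same CMH model, in which every missing Week 12 response counts as non-response, whatever the reason, except for a subject who responds both before and after the window.

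A narrower version would score only infection-related missing data as non-response and leave logistical gaps to MI. It depends on the database separating infection from logistics visit by visit. SAP 9.2.1 says that affected visits will be recorded but not that the two reasons are kept apart. Protocol 6.1 does provide a COVID-19 infection form, but a rule linking it to missed visits would have to be written. The version that covers all missing data needs no such rule.

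The cost is one sentence in the SAP and one extra run. The downside is that the sensitivity estimate may be slightly less favourable than the primary one. If the two agree, the robustness check promised in SAP 9.2.1 has been delivered for this assumption.

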9.2.2 Handling of missing data in Categorical Endpoints

- Non-Responder Imputation incorporating multiple imputation to handle COVID-19 and logistical problems (geo-political restrictions) (NRI-MI) will be the primary approach to handle missing data for categorical endpoints. The

NRI-MI will categorize any subject who does not have an evaluation during a pre-specified visit window (either due to missing assessment or due to early withdrawal from the study) as a non-responder for the visit. The only exceptions are: 1) when the subject is a responder both before and after the visit window, where the subject will be categorized as a responder for the visit, and 2) when the data is missing due to COVID-19 infection or logistical restriction, or logistical problems (geo-political restrictions), which will then be handled by Multiple Imputation. Subjects whose change/percent change from Baseline cannot be calculated because of a missing Baseline will be considered as a non-responder at all post-baseline visits in NRI-MI approach.

- **Multiple Imputation (MI):** a sensitivity analysis for the primary endpoint: Markov Chain Monte Carlo (MCMC) will be first applied to augment data into monotonic missing pattern and PROC MI will be used to generate 30 datasets using the regression method. The variables to be included in the imputation model for the Placebo-Controlled Period are treatment group, stratification factors at randomization [Baseline glucocorticoid (yes/no), number of prior failed b/tsDMARDs (1; 2 or more), and a combined prior anti-TNF failure/adalimumab use factor (prior anti-TNF failure with adalimumab use; prior anti-TNF failure without adalimumab use; no prior anti-TNF failure)], Baseline, and measurements at each visit in the Placebo-Controlled Period. The variables to be included in the imputation model for the LTE periods are treatment group, major stratum [baseline glucocorticoid use (yes/no) and prior adalimumab use (yes/no)], Baseline, and measurements at each visit in the LTE periods. The random seed for MCMC and the random seed for PROC MI are specified in Appendix C. The imputed post-baseline measurements will be rounded to the same precision as the observed data before the determination of responder status. Subjects will be characterized as responders or non-responders based on the MI imputed datasets. Using the Cochran-Mantel-Haenszel (CMH) model adjusted by stratification factors [Baseline glucocorticoid (yes/no), number of prior failed b/tsDMARDs (1; 2 or more), and a combined prior anti-TNF failure/adalimumab use factor (prior anti-TNF failure with adalimumab use; prior anti-TNF failure without adalimumab use; no prior anti-TNF failure)], the imputed endpoints will be analyzed using each of the 30 datasets. SAS PROC MIANALYZE will be used to generate the

final inferences of the risk difference between each ABBV-154 group and placebo.

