4 INVESTIGATIONAL PLAN

4.1 Overall Study Design and Plan

This is a randomized, double-blind, Phase 2b, dose-ranging study with a 12-week Placebo-Controlled Period, a 66-week Double-Blind Long-Term Extension (LTE) Period 1, a 104-week LTE Period 2, and a 70-Day Follow-up Period in adults with moderately to severely active RA and on background MTX, who have had an inadequate response to b/tsDMARDs treatment.

Subjects will remain on a stable dose of MTX until Week 24 (unless qualifying rescue therapy as described in [Section 5.4](#)); thereafter MTX may be adjusted within the range of 7.5 – 25 mg/week. At Baseline, 425 subjects will be randomized to 5 treatment groups in a 1:1:1:1:1 ratio to receive ABBV-154 at either 40 mg, 150 mg, 340 mg, subcutaneously (SC) every other week (eow); 340 mg SC every 4 weeks (e4w); or placebo SC eow. Randomization will be stratified by Baseline glucocorticoid (yes/no); number of prior failed b/tsDMARDs (1; 2 or more); and prior anti-TNF failure (yes/no) and if yes further stratification by prior adalimumab use (yes/no). At the end of the Week 12 Visit, subjects previously on placebo will be re-randomized and will receive ABBV-154 150 mg SC eow or ABBV-154 340 mg SC eow. At re-randomization, subjects will be stratified by baseline glucocorticoid use (yes/no) and prior adalimumab use (yes/no). Subjects from the other dose groups will continue with their respective dose and dosing regimen. The enrollment for subjects with prior adalimumab use is capped at approximately 30% of the total enrolled subjects.

Systemic glucocorticoids (dose of ≤ 7.5 mg/d prednisone equivalent at Baseline) must be tapered off within 4 weeks of the start of study drug.

[figure not shown]
The Primary Analysis will be conducted after all ongoing subjects have completed Week 12 or have withdrawn from the study. After the Primary Analysis, additional analyses may be conducted as needed. A final analysis will be conducted after all subjects have completed LTE Period 2 and a safety follow-up visit or have withdrawn from the study. To maintain integrity of the trial, the study sites and subjects will remain blinded until all subjects have either completed the last visit of LTE Period 1 or have withdrawn from the study. The AbbVie study team will be unblinded to treatment assignment after the Primary Analysis.

The schematic of the study is shown in [Figure 1](#).

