2.2 Study Design Overview

This is a randomized, double-blind, Phase 2b, dose-ranging study with a 12-week Placebo-Controlled Period, a 66-week Long-Term Extension (LTE) Period 1, and a 104-week LTE Period 2 in adults with moderately to severely active RA and on background MTX, who have had an inadequate response to b/tsDMARD treatment.

The Primary Analysis will be conducted after all ongoing subjects have completed Week 12 or withdrawn from the study. After the Primary Analysis, additional analyses may be conducted as needed. A final analysis will be conducted after all subjects have completed the LTE Period 2 and a safety follow-up visit 70 days after the last dose of

study drug, or have withdrawn from the study. The schematic of the study is shown in Figure 1.

Figure 1. Study Schematic

BL = Baseline; EOW = every other week; E4W = every 4 weeks; n = number of subjects; SC = subcutaneous

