2.3 Treatment Assignment and Blinding

Subjects will remain on a stable dose of MTX until Week 24 (unless qualifying for rescue therapy as described in Protocol Section 5.4); thereafter MTX may be adjusted within the range of 7.5 – 25 mg/week. At Baseline, approximately 425 subjects will be randomized to 5 treatment groups in a 1:1:1:1:1 ratio to receive ABBV-154: 40 mg, 150 mg, 340 mg SC EOW; 340 mg SC E4W, or placebo. Randomization will be stratified by Baseline glucocorticoid (yes/no); number of prior failed b/tsDMARDs (1; 2 or more); and prior anti-TNF failure (yes/no) and if yes further stratification by prior adalimumab use (yes/no). At Week 12, subjects assigned to placebo will be re-randomized in a 1:1 ratio to receive ABBV-154 150 mg or 340 mg SC EOW; subjects from the other dose groups will continue with their respective dose and dosing regimen. Re-randomization will be stratified by Baseline glucocorticoid use (yes/no) and prior adalimumab use (yes/no). The

enrollment for subjects with prior adalimumab use is capped at approximately 30% of the total subjects enrolled. Systemic glucocorticoids (dose of ≤ 7.5 mg/d prednisone equivalent at Baseline) must be tapered off within 4 weeks of the start of study drug.

All AbbVie personnel with direct oversight of the conduct and management of the trial (except for AbbVie Drug Supply Management Team) will be blinded to each subject's treatment through Week 12. The AbbVie study team will be unblinded to treatment assignment for the Primary Analysis. This unblinding will take place after all subjects have completed the Week 12 visit or have withdrawn from the study prior to Week 12. To maintain integrity of the trial, the study site personnel and the subjects will remain blinded until all subjects have either completed the last visit of LTE Period 1 or have withdrawn from the study. Blinded dosing regimens will be continued until the previous criteria are met. To maintain the blind, the ABBV-154 and placebo pre-filled syringes provided for the study will be identical in appearance. The IRT will provide access to unblinded subject treatment information in the case of a medical emergency.

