3.0 Endpoints

3.1 Primary Endpoint(s)

The primary endpoint is the achievement of ACR50 at Week 12.

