9.3.2 Analysis of Primary Efficacy Endpoint(s)

The statistical null hypothesis corresponding to the primary endpoint is that there is no difference between an ABBV-154 group and the placebo group response rate in the proportion of subjects achieving ACR50 at Week 12.

Analysis of the primary endpoint will be conducted in the ITT Population based on treatment as randomized using NRI-MI. Comparison of the primary endpoint will be made between each ABBV-154 group and the placebo group using the CMH test adjusting for Baseline glucocorticoid (yes/no), number of prior failed b/tsDMARDs (1; 2 or more), and a combined prior anti-TNF failure/adalimumab use factor (prior anti-TNF failure with adalimumab use; prior anti-TNF failure without adalimumab use; no prior anti-TNF failure)].

The attributes of the estimands corresponding to the primary efficacy endpoint are summarized in Table 1.

Table 1. Summary of the Estimand Attributes of the Primary Efficacy Endpoint(s)

Estimand Label	Attributes of the Estimand				Statistical Summary
	Treatment	Endpoint	Population	Handling of Intercurrent Events (IE)	
Primary: Composite Estimand	ABBV-154 vs. Placebo	Achievement of ACR50 at Week 12	All randomized subjects who received at least one dose of study drug (ITT Population)	IE: none considered	Difference between ABBV-154 and placebo in the proportion of subjects achieving ACR50 at Week 12

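### The before-and-after exception in NRI-MI lets a response on ABBV-154 help score a missing placebo Week 12 outcome as a placebo response

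*SAP*

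**What the plan says.** The primary endpoint is ACR50 at Week 12 (SAP 3.1). SAP 9.3.2 sets the method: "Analysis of the primary endpoint will be conducted in the ITT Population based on treatment as randomized using NRI-MI". SAP 9.4.2 uses NRI-MI for the categorical secondary endpoints as well.

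Under SAP 9.2.2 a subject with no evaluation in the visit window is a non-responder, with two exceptions. The first applies "when the subject is a responder both before and after the visit window"; the missing visit is then scored as a response. The second sends data missing because of COVID-19 or geo-political logistics to multiple imputation. The text does not say which exception prevails if both apply, and it places no limit of period or treatment on the later visit.

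On the treatment switch, SAP 2.3 states: "At Week 12, subjects assigned to placebo will be re-randomized in a 1:1 ratio to receive ABBV-154 150 mg or 340 mg SC EOW". Protocol 4.1 places this at the end of the Week 12 visit. The four ABBV-154 arms keep their regimens.

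On timing, SAP 2.2 states: "The Primary Analysis will be conducted after all ongoing subjects have completed Week 12 or withdrawn from the study". SAP 9.5 provides for binary data after Week 12 to be analysed at that same point.

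**The concern.** For any visit before Week 12, the visits on either side fall within the same randomized treatment, and bridging a single gap is a reasonable convention. Week 12 is different for placebo, because every later scheduled visit lies in the extension. The exception can then use a response to 150 mg or 340 mg eow as evidence that the subject was responding on placebo. Only the placebo arm mixes treatments in this way.

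One placebo arm serves all four comparisons, so any shift in its rate moves all four differences together. The same rates feed the MCP-Mod analysis in SAP 9.6, where the minimum effective dose is read against a 22% target.

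The second problem affects every arm. Early enrollees will have later visits in the database at the Primary Analysis, while the last enrollees may have none. Two subjects with the same record up to Week 12, both of whom go on to respond, can receive different Week 12 scores because of when they enrolled.

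**Working it through.** **Passages side by side**

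1. Protocol Appendix E schedules joint counts, hsCRP, HAQ-DI, pain and the global assessments at Weeks 8, 12, 14 and 18, with none at Week 10. Randomization and study drug administration are both marked at Week 12.
2. A missing Week 12 is therefore bridged from Week 8 or earlier, on placebo, to Week 14 or later.
3. The clear case is a placebo subject who attends Week 12, is re-randomized and dosed, but lacks evaluable ACR data. Week 14 then follows the first ABBV-154 dose.
4. If the whole Week 12 visit is missed, the documents do not say when the switch takes place. A Week 14 assessment made before dosing could still reflect placebo.
5. Elsewhere the SAP keeps the period boundary. The imputation model in 9.2.2 uses only Placebo-Controlled Period measurements for that period and a separate model for the extension, and the MMRM in 9.2.3 is split the same way. SAP 8.0 considers no intercurrent events, so the switch is not dealt with there either.

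**The plan's own figure**

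Inputs from SAP 2.4: 85 per arm, 13% versus 35%, two-sided alpha 0.1, chi-square test.

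- Null SE = √(2 × 0.24 × 0.76 / 85) = 0.0655
- Alternative SE = √((0.13 × 0.87 + 0.35 × 0.65) / 85) = 0.0633
- Power = Φ((0.22 − 1.645 × 0.0655) / 0.0633) = 0.962

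Exact enumeration of the chi-square test gives 0.964. The stated power of at least 90% is reproduced.

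**Size of the effect**

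Expected placebo subjects rescued = 85 × m × q × r, where m is the proportion with Week 12 missing and a later visit seen, q the proportion who responded earlier on placebo, and r the proportion who respond after the switch. The documents give none of these, so the ranges are assumptions.

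| | m | q | r | Subjects | Points on placebo rate |
|---|---|---|---|---|---|
| Low | 2% | 10% | 50% | 85 × 0.001 = 0.09 | 0.1 |
| High | 10% | 20% | 70% | 85 × 0.014 = 1.19 | 1.4 |
| More missingness | 15% | 13% | 90% | 85 × 0.01755 = 1.49 | 1.8 |

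Each rescued subject adds 1/85 = 1.18 points. Taking 13% as the placebo rate without any rescue:

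| Rescued | Placebo rate | Difference (points) | Power |
|---|---|---|---|
| 0 | 13.00% | 22.00 | 0.962 |
| 1 | 14.18% | 20.82 | 0.940 |
| 2 | 15.35% | 19.65 | 0.910 |
| 3 | 16.53% | 18.47 | 0.872 |

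These points are an upper bound on the bias. A subject who responded both before and after Week 12 may truly have been responding at Week 12, and for that subject the exception gives the right answer.

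**The case against.** The strongest reply is that the exception needs several things at once: Week 12 not evaluable, for a reason other than COVID-19 or logistics; an earlier ACR50 response on placebo; a later response after the switch; and that later visit in the database at the cut. Early withdrawals usually have no later visit. The bias raises the placebo rate, so it cannot produce a false claim for ABBV-154. The MI sensitivity analysis of the primary endpoint already avoids the exception. All of this stands, and it is why the effect is small. It does not remove the gap in the rule. The MI analysis changes all other missing-data handling too, so it cannot isolate this effect, and SAP 9.4.3 plans no sensitivity analysis for the binary secondary endpoints.

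It can also be said that the active arms do not switch, so bridging in them is harmless and removing it there goes further than the defect. That is fair as regards mixing treatments. It does not answer the dependence on enrolment date, which affects all arms.

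Two stronger readings are tempting but unsupported. A reader might infer that the placebo rate is contaminated as a matter of fact; the text shows only that it can be. A reader might also infer that the Week 12 test result could change at a later database lock. SAP 9.1 makes the Primary Analysis the sole and final one for the primary and secondary efficacy endpoints, and SAP 9.5 extends those variables to visits other than Week 12. Nothing provides for the Week 12 test to be run again.

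**Conclusion.** The point holds as a gap in the wording of the primary missing-data rule. A response on ABBV-154 can help turn a missing placebo Week 12 outcome into a placebo response, and the scoring can depend on enrolment date. No section of either document closes the gap.

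The expected size is small: at most about 0.1 to 1.4 points on the placebo rate under the first two sets of assumptions above, and 1.8 points with more missingness. The direction is against ABBV-154. Even two rescued subjects would leave power for the design difference at 91.0%. These sizes rest on assumed missingness and response rates, and on reading the later visit as any visit after the window, since 9.2.2 refers to pre-specified windows without defining them there. The change is worth making because it concerns the primary analysis and costs little, not because it threatens the trial's conclusion.

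**What to change.** Add to SAP 9.2.2:

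*For Week 12, exception 1 does not apply in any arm; no assessment after the first LTE-period dose is used to determine Week 12 response.*

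Keep exception 1 for visits before Week 12, and report by arm how many subjects it would have reclassified at Week 12. Applying the sentence to all arms keeps handling symmetric and removes the dependence on the data cut. It also means the Week 12 score no longer turns on when a subject who missed the visit was switched. Restricting it to placebo would leave the enrolment-date problem in the active arms.

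The cost is one sentence and one count. The downside is that some ABBV-154 subjects with an isolated missing Week 12 become non-responders, probably more than in placebo because response is expected to be higher there. For illustration, assume 5% missing, with earlier and later response of 30% and 80% on active drug and 13% and 60% on placebo:

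- Active: 85 × 0.05 × 0.30 × 0.80 = 1.02 subjects, or 1.2 points
- Placebo: 85 × 0.05 × 0.13 × 0.60 = 0.33 subjects, or 0.39 points

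The estimated difference would then fall by about 1.2 − 0.39 = 0.8 points. The SAP should accept that openly.
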